10.4 OBLIGATION OF THE INVESTIGATOR REGARDING SAFETY REPORTING

10.4.1 Definitions of adverse events

10.4.1.1 Adverse event

An AE is any untoward medical occurrence in a patient or clinical investigation patient administered a pharmaceutical product and which does not necessarily have to have a causal relationship with this treatment.

Intensity of an AE is defined as:

- Mild: no modification of daily activities and does not require mandatory corrective/symptomatic treatment
- Moderate: hinders normal daily activities and/or requires mandatory corrective/symptomatic treatment
- Severe: prevents daily activities and requires mandatory corrective/symptomatic treatment

10.4.1.2 Serious adverse event

A SAE is any untoward medical occurrence that at any dose:

- Results in death, or
 - Is life-threatening, or
- Note: The term “life-threatening” in the definition of “serious” refers to an event in which the patient was at risk of death at the time of the event; it does not refer to an event which hypothetically might have caused death if it were more severe.
- Requires inpatient hospitalization or prolongation of existing hospitalization, or
 - Results in persistent or significant disability/incapacity, or
 - Is a congenital anomaly/birth defect
 - Is a medically important event.

Medical and scientific judgment should be exercised in deciding whether expedited reporting is appropriate in other situations, such as important medical events that may not be immediately life-threatening or result in death or hospitalization but may jeopardize the patient or may require medical or surgical intervention (ie, specific measures or corrective treatment) to prevent one of the other outcomes listed in the definition above.

Note: The following list of medically important events is intended to serve as a guideline for determining which condition has to be considered a medically important event. The list is not intended to be exhaustive:

- Intensive treatment in an ER or at home for:
 - Severe hypersensitivity reactions (anaphylaxis, allergic bronchospasm [see [Appendix I](#) for the clinical criteria for diagnosing anaphylaxis])
 - Blood dyscrasias (ie, agranulocytosis, aplastic anemia, bone marrow aplasia, myelodysplasia, pancytopenia),
 - Convulsions (seizures, epilepsy, epileptic fit, absence, etc).
- ALT >3 x ULN + TBILI >2 x ULN or asymptomatic ALT increase >10 x ULN. See [Appendix K](#).
- Suicide attempt or any event suggestive of suicidality.
- Syncope, loss of consciousness (except if documented as a consequence of blood sampling)
- Bullous cutaneous eruptions.
- Cancers diagnosed during the study or recurs during the study
- Chronic neurodegenerative diseases (newly diagnosed) or aggravated during the study (only if judged unusual/significant by the Investigators in studies assessing specifically the effect of a study drug on these diseases).

- Suspected transmission of an infectious agent via a medicinal product (eg, product contamination).

10.4.1.3 Adverse event of special interest

An AESI is an AE (serious or non-serious) of scientific and medical concern specific to the Sponsor's product or program, for which ongoing monitoring and immediate notification by the Investigator to the Sponsor is required. Such events may require further investigation in order to characterize and understand them. Adverse events of special interest may be added, modified or removed during a study by protocol amendment.

- Pregnancy of a female subject entered in a study as well as pregnancy occurring in a female partner of a male subject entered in a study with IMP.

Pregnancy occurring in a female patient entered in the clinical trial or in a female partner of a male patient entered in the clinical trial. It will be qualified as an SAE only if it fulfills one of the seriousness criteria (see [Section 10.4.1.2](#)).

- In the event of pregnancy in a female participant, IMP should be discontinued.
- Follow-up of the pregnancy in a female participant or in a female partner of a male participant is mandatory until the outcome has been determined.
- Symptomatic overdose (serious or non-serious) with IMP:
 - An overdose (accidental or intentional) with the IMP is an event suspected by the Investigator or spontaneously notified by the patient and defined as at least twice the intended dose given during a 4 day period.

Of note, asymptomatic overdose has to be reported as a standard AE.

- ALT > 3 x ULN: If increase in ALT >3 x ULN, see the "Increase in ALT" flow chart in [Appendix K](#) of the protocol.
 - However, if the increase in ALT is ≥ 2 x the baseline value (with baseline ALT \geq ULN) but ≤ 3 x ULN, then ALT should be re-tested within 72 hours of initial sample to determine if the retest value meets the AESI criterion of ALT > 3 x ULN. If so, proceed as above and follow the guidelines of [Appendix K](#). If not, monitoring of the laboratory findings will be up to the medical judgment of the Investigator.

- Other project specific AESI(s):
 - [REDACTED]

- Anaphylactic reactions or acute allergic reactions that require immediate treatment (refer to [Appendix I](#) for definition of Anaphylaxis)
- Severe injection site reactions (see [Appendix J](#))
- Tuberculosis or initiation of medications for suspected tuberculosis
- Acute renal failure (see [Appendix K](#)).

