c Study treatment is to be administered once a week, either at the site or at home by a qualified healthcare professional – Last dose will be given at Week 23

d Complete physical examinations will include skin, nasal cavities, eyes, ears, respiratory, cardiovascular, gastrointestinal, neurological, lymphatic, and musculoskeletal systems. For the dermatological examination the Investigator should evaluate for SSc related skin changes and some specific findings that may indicate vasculitis including, but not limited to: purpura, papules or non-blanching rashes. Nail beds (periungual areas) should be examined for “splinter lesions” and digital tuft for tuft purpura or ischemia. Gynecological and urogenital examinations will not be done in this study unless for cause

e Vital signs, including blood pressure (mmHg), heart rate (beats per minute) and body weight (kg) will be measured at screening, baseline and every subsequent visit. Height (cm) will be measured at screening (Visit 1) only. BMI will be calculated automatically at all visits

- f* All abnormal ECG interpretation will be reviewed and confirmed by a local cardiologist.
- g* Previous echocardiogram may be used if obtained within 6 months of V1 (screening visit).
- h* Hematology: Hemoglobin, hematocrit, red blood cell count, erythrocyte sedimentation rate (ESR), white blood cell count with differential and platelet count. Biochemistry: Fasting glucose, blood urea nitrogen, creatinine, sodium, potassium, chloride, bicarbonate, calcium, phosphorous, total protein, albumin, total bilirubin, alkaline phosphatase, ALT, AST, CPK, hs CRP. Urinalysis (dipstick) to include: specific gravity, pH, glucose, ketones, blood, protein, nitrate, leukocyte esterase, urobilinogen and bilirubin. If any parameter on the dipstick is abnormal, a urine sample should be sent to the central laboratory for testing. If positive for protein and/or red blood cells, microscopic analysis will be performed by the central laboratory
- i* Serology testing includes HIV-1/HIV-2 antibody, hepatitis B surface antigen, hepatitis B surface antibody, hepatitis B core antibody, hepatitis B DNA (reflex to a positive hepatitis B core antibody), hepatitis C antibody and hepatitis C RNA (reflex to a positive hepatitis C antibody)
- j* [REDACTED]

- k* Tuberculosis screen: history and QuantiFERON-TB Gold test. If the result of the initial QuantiFERON-TB Gold test is indeterminate, the test should be repeated one time

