8.1.2 Dose of drug per administration

- SAR156597 group: 1 injection of SAR156597 200 mg administered subcutaneously qw.
- Placebo group: 1 injection of placebo administered subcutaneously qw.

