8.1.4 Route and method of administration

The route and method of administration are SC in the abdomen. SC injection sites should be alternated between the 4 quadrants of the abdomen (avoiding navel and waist areas) so that the same site is not injected for two consecutive weeks. The exact site of each injection will be documented on the source document. It is recommended that the injection occur at a site free of SSc involvement, if possible.

The IMP is administered every 7 days ± 2 days from initial IMP administration. This window is permitted per protocol to accommodate various circumstances (eg, pending laboratory results, management of AE, visit scheduling difficulty). The IMP administration should be performed by other site personnel, blinded from the person in charge of the preparation of the solutions and syringes.

If IMP administration is missed or temporarily discontinued, the initial schedule of injections may be resumed upon the investigator's medical judgment and discretion while the missed dose(s) will not be administered. This does not apply to permanent treatment discontinuation.

On days when the patient has a study visit, the IMP will be administered by the Investigator or delegate after clinic procedures and blood collection.

For doses not administered at the study site, the IMP will be administered by qualified site personnel and /or healthcare professionals (eg, visiting nurse service).

Patients should be monitored by site personnel/visiting nurse for at least 30 minutes or up to 2 hours as per country specific requirements after each administration for potential signs and symptoms that may suggest a hypersensitivity reaction.

For doses not given at the study site, a booklet will be provided to the patient to record information related to the injections; this booklet will be completed by the visiting nurse after each injection and will be kept as source data in the patient's study file. Patients will be instructed to bring the booklet back at the subsequent site visit for Investigator's review.

Between the protocol-scheduled on-site visits, interim visits to the site may be required for IMP dispensing. As an alternative to these visits, the IMP may be supplied from the site to the patient via a Sponsor-approved courier company where allowed by local regulations and approved by the patient.

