2.4.3.2 Compliance

A given administration will be considered non-compliant if the patient did not take the planned dose of treatment as required by the protocol. No imputation will be made for patients with missing or incomplete data.

Overall percentage of compliance for a patient will be defined as $100 - (\% \text{ days with below-planned dosing} + \% \text{ days with above-planned dosing})$, considering that injections should be performed every week ± 2 days as per protocol.

Above-planned dosing percentage for a patient will be defined as $100 * \text{the number of days with more than 1 injection administration within the 5 days before divided by the duration of IMP injection exposure in days}$.

Below-planned dosing percentage for a patient will be defined as $100 * \text{the number of days with no injection administration within the previous 9 days divided by the duration of IMP injection exposure in days}$.

Treatment compliance, above-planned, and under-planned dosing percentages will be summarized descriptively as quantitative variables (number, mean, SD, median, minimum, and maximum). The percentage of patients whose compliance is $<80\%$ will be summarized. In addition, numbers and percentages of patients with $[0;5]$, $]5;10]$, $]10;20]$, and $>20\%$ of days with above or under-planned dosing will also be provided.

In addition, the following parameters will be summarized by treatment arm:

- The number of advanced injections (≤ 3 days apart from the previous injection, 4 days apart from the previous injection) and the number of delayed injections (more than 9 days between two consecutive injections).
- The number of patients with at least one advanced injection and the number of patients with at least one delayed injection. A patient could be counted in several categories.
- The frequency of IMP injections (mean (SD), median, Min:Max description) will be defined for each patient as the average number of days between two consecutive injections: $(\text{last injection date} - \text{first injection date}) / (\text{number of injections} - 1)$ for patients with at least 2 injections.

Cases of overdose are reported in the AE e-CRF pages as AESI if symptomatic or AE if asymptomatic. The reported cases of overdose will be described in the AE analysis (see [Section 2.1.5](#) and [Section 2.4.5.1](#)).

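### Two weekly injections inside the protocol's own dosing window can be 3 days apart, which meets the dose/time threshold for overdose and breaks the SAP's compliance limits.

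*Protocol*

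**What the plan says.** Protocol 8.1.4 sets the schedule: "The IMP is administered every 7 days ± 2 days from initial IMP administration". It adds: "This window is permitted per protocol to accommodate various circumstances". After a missed or interrupted dose, it allows the original injection schedule to be picked up again.

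Protocol 8.1.2 gives the dose: "SAR156597 group: 1 injection of SAR156597 200 mg administered subcutaneously qw". The flow chart (Protocol 1.2) states: "Last dose will be given at Week 23". With the first dose on Day 1, that makes 24 weekly doses.

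Protocol 10.4.1.3 gives a two-part description of overdose. It is an "event suspected by the Investigator or spontaneously notified by the patient", and it is "defined as at least twice the intended dose given during a 4 day period". Symptomatic overdose is an AESI, notifiable within 24 hours (Protocol 10.4.5). For the rest: "Of note, asymptomatic overdose has to be reported as a standard AE". The section does not mention the dosing window.

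SAP 2.4.3.2 repeats the reporting split: "Cases of overdose are reported in the AE e-CRF pages as AESI if symptomatic or AE if asymptomatic". The same section refers to the protocol's weekly ±2-day window. It then measures above-planned dosing over a 5-day look-back and below-planned dosing over a 9-day look-back. It counts injections 3 days or less, or 4 days, after the previous one as advanced, and those more than 9 days after it as delayed. SAP 2.1.5.1 identifies symptomatic overdose from a tick box on the AE page of the e-CRF.

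**The concern.** A pair of injections should not be on schedule under one section and at the overdose threshold under another. Here it can be. One site may follow 8.1.4 and see compliant dosing; another may follow 10.4.1.3 and file an AE, or an expedited AESI if there are symptoms. Some reported overdoses could then reflect how a site read the text and not a dosing error.

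The compliance summary has a related problem. It cites the protocol's window but applies limits that do not follow from the protocol's wording, so permitted dosing can lower a patient's compliance percentage.

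**Working it through.** **Inputs.** Interval 7 days, window ±2 days, anchored at the first injection (Protocol 8.1.4). Dose 200 mg (8.1.2). 24 doses, numbered k = 0 to 23, hence 23 consecutive pairs (Protocol 1.2). Overdose threshold: twice the dose in 4 days (10.4.1.3). Limits of 5 and 9 days (SAP 2.4.3.2).

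**Step 1: reproduce the SAP's limits.** If the window runs from the *previous* injection, the permitted gap is 7 − 2 = 5 to 7 + 2 = 9 days. These are the SAP's two limits exactly.

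**Step 2: gaps under the protocol's wording.** Dose k (k ≥ 1) may fall from day 7k − 2 to day 7k + 2 after the first.

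- Smallest gap: [7(k+1) − 2] − [7k + 2] = 3 days.
- Largest gap: [7(k+1) + 2] − [7k − 2] = 11 days.
- First pair only (dose 0 is fixed): 5 to 9 days.

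So 22 of the 23 pairs may be anywhere from 3 to 11 days apart with both doses in window.

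**Step 3: compare with the overdose threshold.** Two doses are 2 × 200 = 400 mg, or 2.0 times the intended dose.

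| Gap | Elapsed time | Calendar days, inclusive | Within 4 days? |
|---|---|---|---|
| 3 days | 72 h | 4 | Yes, on either count |
| 4 days | 96 h | 5 | Only by elapsed time |
| 5 days | 120 h | 6 | No |

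Under a previous-injection anchor the smallest gap is 5 days, and no in-window pair meets the threshold.

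**Step 4: which combinations are involved.** With whole-day offsets of −2 to +2 for each dose there are 5 × 5 = 25 combinations. One gives a 3-day gap and two give a 4-day gap. Two give a 10-day gap and one an 11-day gap. So 6 of 25 permitted combinations fall outside the SAP's 5-to-9-day range. This counts combinations; it is not a probability.

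**Step 5: effect on compliance.** Take each look-back as excluding the day itself. With injections on days 0 and 3, days 4 and 5 each have two injections in the previous 5 days, so 2 days count as above-planned. A 4-day gap costs 1 day. By the same logic a 10-day gap costs 1 below-planned day and an 11-day gap costs 2. Full exposure is 23 × 7 + 7 = 168 days, so one 3-day or 11-day gap lowers compliance by 2/168 = 1.2 percentage points. To fall below the SAP's 80% line on permitted dosing alone, a patient would need about 17 such gaps (34/168 = 20.2%) among the 22 available.

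**The case against.** **The definition has two parts.** A close pair must also be suspected by the Investigator or notified by the patient. Symptomatic cases come from a tick box, and nothing in the SAP derives an overdose from injection dates. This stands. A reader might infer that every in-window 3-day pair is automatically an overdose AE or AESI; the documents do not support that. They support only that such a pair meets the dose/time part of the definition and may be reported.

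**The window may have been meant from the previous injection.** The SAP's limits fit that reading, and Protocol 8.7.1 speaks of weekly intervals between visits. If it was intended, the overlap with overdose disappears. But 8.1.4 names the initial administration and allows the initial schedule to be resumed. Protocol 10.1 also fixes visits relative to randomization with the same ±2 days, and doses due on visit days are given at the visit. The protocol's text describes a fixed calendar, so the protocol and SAP differ as written.

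**A patient count is tempting.** Assume independent offsets, with +2 and −2 each having probability p, and let f(n) be the chance of no +2-then-−2 sequence in n doses. Then f(n) = f(n−1) − p²·f(n−2), with f(0) = f(1) = 1. For n = 23 and p = 0.02, 0.05, 0.10 and 0.20, the share of patients with at least one 3-day pair is 0.9%, 5.4%, 20.0% and 60.8%. Every p is an assumption, because the documents give no distribution of dosing days. The window is also described as an accommodation for particular circumstances, which makes the top value hard to defend. The result counts close pairs, not reported overdoses, so it shows only that the size is unknown.

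**The overdose rate may still be readable.** A reader might conclude that it becomes uninterpretable. That goes too far. SAP 2.4.3.2 already tabulates close injections by arm from recorded dates, and nothing in the window's wording favours one arm. What is missing is a split between in-window and out-of-window pairs.

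**Conclusion.** The inconsistency is real and minor. On the protocol's wording, 22 of 23 consecutive pairs can be 3 days apart with both doses permitted, and a 3-day pair meets the dose/time threshold for overdose however the days are counted. On-protocol dosing could therefore be reported as overdose, possibly inconsistently across sites. How often this would happen cannot be estimated from the documents.

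Separately, SAP 2.4.3.2 would mark some permitted injections as above-planned, advanced or delayed, at a cost of at most 1.2 percentage points of compliance per gap at full exposure.

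The conclusion rests on taking the anchor in 8.1.4 literally. The compliance figure also rests on the look-back convention in Step 5. The consequences stay within descriptive safety and compliance tables; the primary efficacy analysis and the sample size are not touched.

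**What to change.** Reconcile Protocol 8.1.4, Protocol 10.4.1.3 and SAP 2.4.3.2 on two matters: the date from which the ±2 days is counted, and how the window relates to the overdose definition. After that, no pair of injections should be both permitted and at the overdose threshold, or both permitted and non-compliant. Which rule should give way is for the sponsor to decide; none is proposed here.

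In SAP 2.4.5.1, split reported overdoses, symptomatic and asymptomatic, by whether both injections were inside the protocol window. SAP 2.5.1 shows that administration dates are recorded on the IMP administration page of the case report form, so no new data are needed and the split is possible whatever the stage of dosing.

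The cost is one protocol clarification, matching wording in the SAP's compliance section, and one extra row in an AE table.

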10.4.2 Serious adverse events waived from expedited regulatory reporting to regulatory authorities

Disease progression is anticipated for the disease being treated (ie, dcSSc) and will be considered expected for the purpose of regulatory reporting. Conversely, an event more severe than the anticipated course of usual disease progression is to be considered unexpected and should be reported.

If a serious and unexpected adverse event occurs for which there is evidence suggesting a causal relationship between the drug and the event (SUSAR), the event must be reported, even if it is a component of the study endpoint.

10.4.3 General guidelines for reporting adverse events

- All AEs, regardless of seriousness or relationship to IMP, spanning from the signature of the informed consent form until the end of the study as defined by the protocol for that patient, are to be recorded on the corresponding screen(s) of the e-CRF.
- Whenever possible, diagnosis or single syndrome should be reported instead of symptoms. The Investigator should specify the date of onset, intensity, action taken with respect to IMP, corrective treatment/therapy given, additional investigations performed, outcome, and his/her opinion as to whether there is a reasonable possibility that the AE was caused by the IMP or by the study procedure(s).
- The Investigator should take appropriate measures to follow all AEs until clinical recovery is complete and laboratory results have returned to normal, or until progression has been stabilized, or until death, in order to ensure the safety of the patients. This may imply that observations will continue beyond the last planned visit per protocol, and that additional investigations may be requested by the monitoring team up to as noticed by the Sponsor.
- When treatment is prematurely discontinued, the patient's observations will continue until the end of the study as defined by the protocol for that patient.
- Laboratory, vital signs or ECG abnormalities are to be recorded as AEs only if:
 - Symptomatic and/or
 - Requiring either corrective treatment or consultation, and/or
 - Leading to IMP discontinuation or modification of dosing, and/or
 - Fulfilling a seriousness criterion, and/or
 - Defined as an AESI

Instructions for AE reporting are summarized in [Table 3](#).

10.4.4 Instructions for reporting serious adverse events

In the case of occurrence of an SAE, the Investigator or any designees must immediately:

- ENTER (within 24 hours) the information related to the SAE in the appropriate screens of the e-CRF; the system will automatically send a notification to the monitoring team after approval of the Investigator within the e-CRF or after a standard delay.
- SEND (preferably by fax or e-mail) a photocopy of all examinations carried out and the dates on which these examinations were performed, to the representative of the monitoring team whose name, fax number, and email address appear on the clinical trial protocol. Care should be taken to ensure that the patient's identity is protected and the patient's identifiers in the clinical trial are properly mentioned on any copy of a source document provided to the Sponsor. For laboratory results, include the laboratory normal ranges.
- All further data updates should be recorded in the e-CRF as appropriate, and further documentation as well as additional information (for laboratory data, concomitant medications, patient status, etc) should be sent (by fax or e-mail) to the monitoring team within 24 hours of knowledge of the SAE. In addition, every effort should be made to further document any SAE that is fatal or life-threatening within a week (7 days) of the initial notification.
- A back-up plan (using a paper CRF process) is available and should be used when the e-CRF system does not work.

Any SAE brought to the attention of the Investigator at any time after the end of the study for the patient and considered by him/her to be caused by the IMP with a reasonable possibility, should be reported to the monitoring team.

